10.0 Drug Formulation And Procurement

10.1 Decitabine

10.1.1 Other Names

Dacogen

10.1.2 Classification

Antineoplastic

10.1.3 Mode of Action

May cause hypomethylation of DNA and cellular differentiation or apoptosis by phosphorylation and direct incorporation into DNA.

10.1.4 Metabolism

Routes of decitabine metabolism and elimination are unknown. Elimination of decitabine is believed to occur through deamination by cytidine deaminase. The effects of renal or hepatic impairment on decitabine pharmacokinetic parameters have not been studied.

10.1.5 Storage and Stability

Store vials at 25°C (77°F); excursions permitted to 15 - 30°C (59 - 86°F).

Unless used within 15 minutes of reconstitution, the diluted solution must be prepared using cold (2°C - 8°C) infusion fluids and stored at 2°C - 8°C (36°F - 46°F) for up to a maximum of 7 hours until administration.

10.1.6 Dose Specifics

For the purposes of this study, decitabine will be given at a dose of 10 mg/m² on days 1-5 of each treatment course.

Decitabine for Injection is supplied as a sterile lyophilized white to almost white powder, in a single-dose vial, packaged in cartons of 1 vial. Each vial contains 50 mg of decitabine.

10.1.7 Preparation

Decitabine is a cytotoxic drug and, as with other potentially toxic compounds, caution should be exercised when handling and preparing decitabine.

Decitabine should be aseptically reconstituted with 10 mL of Sterile Water for Injection (USP); upon reconstitution, each mL contains approximately 5.0 mg of decitabine at pH 6.7-7.3. Immediately after reconstitution, the solution should be further diluted with 0.9% Sodium Chloride Injection, 5% Dextrose Injection, or Lactated Ringer's Injection to a final drug concentration of 0.1 - 1.0 mg/mL.

Unless used within 15 minutes of reconstitution, the diluted solution must be prepared using cold (2°C - 8°C) infusion fluids and stored at 2°C - 8°C (36°F - 46°F) for up to a maximum of 7 hours until administration.

10.1.8 Administration

Patients may be pre-medicated with standard anti-emetic therapy per institutional guidelines.

10.1.9 Availability

Commercially available

10.1.10 Side Effects

Pregnancy category D

Decitabine may cause fetal harm when administered to a pregnant woman. Women of childbearing potential should be advised to avoid becoming pregnant while using Decitabine. Men should be advised not to father a child while receiving treatment with Decitabine, and for 2 months afterwards.

The most commonly occurring adverse reactions include neutropenia, thrombocytopenia, anemia, fatigue, pyrexia, nausea, cough, petechiae, constipation, diarrhea, and hyperglycemia.

10.2 Vorinostat (SAHA)

10.2.1 Other Names

Suberoylanilide hydroxamic acid, zolinza

10.2.2 Classification

Histone deacetylase (HDAC) inhibitor

10.2.3 Mode of Action

Inhibits the enzyme histone deacetylase (HDAC), induces differentiation in some cell types, and has been shown to induce p53-independent apoptosis

10.2.4 Metabolism

The major pathways of Vorinostat metabolism involve glucuronidation and hydrolysis followed by β -oxidation. *In vitro* studies using human liver microsomes indicate negligible biotransformation by cytochromes P450 (CYP).

10.2.5 Elimination

Vorinostat is eliminated predominantly through metabolism with less than 1% of the dose recovered as unchanged drug in urine, indicating that renal excretion does not play a role in the elimination of Vorinostat.

10.2.6 Storage and Stability

Store it at room temperature and away from excess heat and moisture.

10.2.7 Dose Specifics

For the purposes of this study, the Vorinostat dose will be 200 mg twice a day days 6-15 of each treatment course.

10.2.8 Administration

Swallow the capsules whole; do not open, chew, or crush them. Take with food same times each day.

10.2.9 Availability

Commercially available; however study funds may cover the cost of the drug if not paid for by the patient's 3rd party payer.

10.2.10 Drug Interactions

Coumarin-derivative anticoagulants: Prolongation of prothrombin time and International Normalized Ratio have been observed with concomitant use.

10.2.11 Side Effects

Pregnancy category D

Vorinostat can cause fetal harm when administered to a pregnant woman. There are no adequate and well controlled studies of Vorinostat in pregnant women. Results of animal studies indicate that Vorinostat crosses the placenta and is found in fetal plasma at levels up to 50% of maternal concentrations. Doses up to 50 and 100 mg/kg/day were tested in rats and rabbits, respectively (~0.5 times the human exposure based on AUC_{0-24 hours}). Treatment related developmental defects included decreased mean live fetal weights, incomplete ossification of the skull, thoracic vertebra, sternum, and skeletal variations (cervical ribs, supernumerary ribs, vertebral count and sacral arch variations) in rats at the highest dose of Vorinostat tested. Reductions in mean live fetal weight and an elevated incidence of incomplete ossification of the metacarpals were seen in rabbits dosed at 150 mg/kg/day. The no observed effect levels for these findings were 15 and 50 mg/kg/day (<0.1 times the human exposure based on AUC) in rats and rabbits, respectively.

Common (Occurring in \geq 20%) : weight decrease, anorexia, diarrhea, nausea, altered taste sensation, fatigue, thrombocytopenia, muscle spasms

Uncommon (in 5-19%): peripheral edema, alopecia, pruritus, dizziness or headache, shivering, raised serum creatinine, cough, upper respiratory infection, anemia

Rare: prolonged QT (3.5 – 6%), DVT/PE

10.3 Interleukin-2 (IL-2)

10.3.1 Other Names

Aldesleukin (modified human recombinant interleukin-2)

10.3.2 Classification

Antineoplastic agent, Immunotherapy, Cytokine

10.3.3 Category

Biologic Response Modifier Agent

10.3.4 Mechanism of Action

- Systemic: Aldesleukin has been shown to possess the biological activity of human native interleukin-2. In vitro studies performed on human cell lines demonstrate the immunoregulatory properties of aldesleukin, including:

- Enhancement of lymphocyte mitogenesis and stimulation of long-term growth of human interleukin-2 dependent cell lines;
 - Enhancement of lymphocyte toxicity;
 - Induction of killer cell (lymphokine-activated killer [LAK] cells and natural killer [NK] cells) activity; and
 - Induction of interferon-gamma production.
- The in vivo administration of aldesleukin in select murine tumor models and in the clinic produces multiple immunological effects in a dose-dependent manner. These effects include activation of cellular immunity with profound lymphocytosis, eosinophilia, and thrombocytopenia, and the production of cytokines, including tumor necrosis factor, interleukin-1 and gamma interferon. In vivo experiments in murine tumor models have shown inhibition of tumor growth. However, the exact mechanism by which aldesleukin mediates its antitumor activity in animals and humans is unknown.
- Aldesleukin causes a capillary leak syndrome (CLS) as a result of increased capillary permeability, leading to extravasation of plasma proteins and fluid into the extravascular space and contributing to loss of vascular resistance. Interleukin-2 has been reported to reversibly decrease serum cholesterol concentrations. Interleukin-2 has been reported to transiently decrease serum testosterone and dihydroepiandrosterone concentrations and to transiently increase plasma estradiol concentrations. It has also been reported to transiently increase adrenal secretion of ACTH and cortisol.

10.3.5 Metabolism

Systemic: 85 min.

10.3.6 Dose Specifics

For the purposes of this study, subcutaneous IL-2 6 million units per dose will be given on days 17, 19 and 22 of each treatment course. Dose for patients weighing less than 45 kg: 3 million units/m² per dose using the same schedule and route

10.3.7 Dose Forms and Strengths

Lyophilized vials containing 22 million units of IL-2

10.3.8 Reconstitution and Syringe Preparation

U of MN patients only (IL-2 for product activation plus 3 injections at 6 million units/dose):

Reconstitute IL-2 vial with 1.2ml sterile water for injection

Add 1.2ml 0.1% albumin in 5% dextrose to IL-2 vial

Yield: 9 million units/ml solution.

Repeat with 2nd vial

Using a 1ml syringe and 18 gauge needle, withdraw 0.56 ml IL-2 from one vial.

Add to an empty, sterile, 10ml vial

Add 3.44ml 0.1% albumin in 5% dextrose.

Yield 5 million units/4ml vial for pheresis product.

Withdraw the remaining contents from the two IL-2 vials into a 10ml syringe, using an 18 gauge needle. Pull the contents from the needle into the syringe.

Attach a syringe tip connector to the 10ml syringe.

Withdraw 0.72 ml dose into a 1ml syringe. Attach luer tip to syringe. Syringe contains a 0.05ml overfill to fill the needle when attached.

Repeat for a total of 3 doses.

Mayo Clinic patients only (IL-2 for pheresis product):

To be prepared by University of Minnesota Medical Center, Fairview IDS

IL-2 will be reconstituted and prepared by Using a 1ml syringe and 18 gauge needle, withdraw 0.56 ml IL-2 from one vial.

Add to an empty, sterile, 10ml vial

Add 3.44ml 0.1% albumin in 5% dextrose.

Yield 5 million units/4ml vial for pheresis product.

Mayo Clinic patients only (IL-2 preparation for patient use):

To be prepared at the Mayo Clinic

Reconstitute IL-2 vial with 1.2ml sterile water for injection

Add 1.2ml 0.1% albumin in 5% dextrose to IL-2 vial

Yield: 9 million units/ml solution

Withdraw the contents from the IL-2 vial into a 10ml syringe, using an 18 gauge needle. Pull the contents from the needle into the syringe.

Attach a syringe tip connector to the 10ml syringe.

Withdraw 0.72 ml dose into a 1ml syringe. Attach luer tip to syringe. Syringe contains a 0.05ml overfill to fill the needle when attached.

Repeat for a total of 3 doses. Label the last filled syringe with the actual dose and as dose #3, in the event this dose is short.

10.3.9 Administration

IL-2 will be administered as an outpatient for three doses no sooner than 2 hours after the NK cell infusion on day 17, and again on days 19 and 22. Pre-medication with acetaminophen 650 mg PO and diphenhydramine 25 mg PO/IV before and 4 hours after each dose of IL-2 is recommended.

10.3.10 Availability

IL-2 will be provided for the purposes of this study.

10.3.11 Warnings and Precautions

- patients with a history of cardiac disease exhibiting a normal thallium stress test
- patients with a history of pulmonary disease exhibiting normal pulmonary function tests
- severe hypotension (due to capillary leak syndrome)
- impaired neutrophil function (reduced chemotaxis)
- increased risk of disseminated infection
- kidney and liver function impairment (avoid concurrent administration with nephrotoxic or hepatotoxic drugs)
- mental status changes
- exacerbation of preexisting autoimmune diseases or initial presentation of autoimmune and inflammatory disorders
- may increase the risk of allograft rejection in transplant patients (due to enhancement of cellular immune function)
- cardiac, pulmonary, renal, hepatic, or central nervous system impairment
- patients with a history of seizures
- Pregnancy Category C

11.0 Adverse Event Reporting

Toxicity and adverse events will be classified according to NCI's Common Terminology Criteria for Adverse Events V 4.0 (CTCAE) and reported on the schedule below. A copy of the CTCAE can be downloaded from the CTEP home page (http://ctep.cancer.gov/protocolDevelopment/electronic_applications/ctc.htm#ctc_40).

Note: throughout this section the generic term “study drug” refers to the study related treatment (Vorinostat/Decitabine, NK cell infusions and IL-2 injections).

11.1 Definitions

The following definitions are based on the Code of Federal Regulations Title 21 Part 312.32 (21CFR312.32(a)).

Adverse Event: Any untoward medical occurrence associated with the use of a drug in humans, whether or not considered drug related.

Suspected Adverse Reaction: Any adverse event for which there is a reasonable possibility that the drug caused the adverse event.

Life-Threatening Adverse Event Or Life-Threatening Suspected Adverse Reaction: An adverse event or suspected adverse reaction is considered “life-threatening” if, in the view of either the investigator or sponsor, its occurrence places the patient or subject at immediate risk of death.

Serious Adverse Event Or Serious Suspected Adverse Reaction: An adverse event or suspected adverse reaction is considered “serious” if, in the view of either the investigator or sponsor, it results in any of the following outcomes:

- Death
- A life-threatening adverse event
- Inpatient hospitalization or prolongation of existing hospitalization
- A persistent or significant incapacity or substantial disruption of the ability to conduct normal life functions
- A congenital anomaly/birth defect.

Important medical events that may not result in death, be life-threatening, or require hospitalization may be considered serious when, based upon appropriate medical judgment, they may jeopardize the patient or subject and may require medical or surgical intervention to prevent one of the outcomes listed in this definition.

If either the IND sponsor or the investigator believes the event is life-threatening or serious, the event must be evaluated by the sponsor for expedited reporting (21CFR 312.32(a)).

Unexpected adverse event or unexpected suspected adverse reaction: An adverse event or suspected adverse reaction is considered “unexpected” if it is not listed in the investigator brochure or is not listed at the specificity or severity that has been observed; or, if an investigator brochure is not required or available, is not consistent with the risk information described in the general investigational plan or elsewhere in the current application, as amended. Thus, adverse events that occur as part of the disease process (including relapse/progress and death from

such) or underlying medical conditions are considered *unexpected*; however, they will not be reportable per section 11.4.

Unanticipated (unexpected) problems/events as defined by the University Of Minnesota IRB are those that are *not* already described as potential risks in the consent form, *not* listed in the Investigator’s Brochure or *not* part of an underlying disease.

Expedited (Rapid) Reporting: Certain events may require rapid notification to entities providing patient safety oversight (e.g. IRB, FDA) as detailed in section 11.4.

11.2 Adverse Event Documentation

Adverse events occurring after the initiation of any study treatment must be documented. Adverse events attributed to a study-related procedure which occur prior to the initiation of study treatment must be documented as well. Refer to appendix VII for a list of expected toxicities.

For the purposes of this study, adverse event documentation requirements will be determined based on grade, expectedness and relationship to study therapy as follows:

	Grade 1	Grade 2		Grade 3		Grade 4 and 5
	Expected or Unexpected	Expected	Unexpected	Expected	Unexpected	Expected or Unexpected
Unrelated Unlikely	Not required	Not required	Not required	Not required	Required	Required
Possible Probable Definite	Not required	Not required	Required	Required non-hematological	Required	Required
				Not required - hematologic events		

All patients will be monitored from the initiation of any study treatment through day 45 after the last dose of study treatment or the start of a new treatment, whichever occurs earlier, as it is expected that most treatment related adverse events will occur during this period. However, the investigator is obligated, upon knowledge of, to report any adverse event considered to be related to study treatment meeting the expedited reporting criteria in section 11.4.

In addition, adverse event collection will include targeted adverse events and unexpected adverse events at specific time points in relation to the NK cell infusion and post NK cell infusion IL-2 injections.

Targeted adverse events (Appendix IX) and unexpected events will be collected at the following time points. Adjust the day to match the time point description. All time points are 24 hours +/- 2 hours.

- Post-Chemo/Pre-NK cell infusion (day 17)
- A single assessment 1-2 hours post NK cell infusion/pre IL-2 injection (day 17)
- pre IL-2 dose 2
- pre IL-2 dose 3
- 48 hours post IL-2 dose 3 (or to coincide with day 24 clinic visit)
- 1 week after last IL-2 dose (or to coincide with day 31 clinic visit)

At each time point, the worst grade of the targeted toxicity since the last assessment or the previous 24 hours (whichever is shorter) will be recorded in addition to any unexpected toxicities felt at least possibly related to the NK cells and/or the IL-2.

In addition, although not always a reportable event, deaths will be recorded in OnCore upon knowledge in the follow-up tab.

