7.5 IL-2 (begin day 17)

Start subcutaneous IL-2 approximately 2 hours, but no earlier than 2 hours, after the NK cell infusion in the absence of grade 4 infusion related toxicity.

If the patient has experienced grade 4 infusion related toxicity and it resolves to grade 2 or better, the IL-2 may be started up to 48 hours after the NK infusion. If no IL-2 is given, the patient will be replaced for statistical analysis.

IL-2 administration: IL-2 will be given at 6 million units on days 17, 19 and 22. For patients weighing less than 45 kilograms, the IL-2 will be given at a dose of 3 million units/m² on days 17, 19 and 22. For the purposes of outpatient scheduling and/or possible delay in treatment start, dosing may be altered to avoid weekends as long as IL-2 is not given on consecutive days and completed within a week.

Pre-medication with acetaminophen 650 mg PO and diphenhydramine 25 mg PO/IV before and 4 hours after each dose of IL-2 is recommended.

Monitoring during IL-2 administration: Patients are monitored for IL-2 related toxicities on a daily basis in clinic until the day after the final IL-2 administration with increased monitoring as clinically required.

IL-2 dose-adjustment for individual patient intolerance: Fevers, rash and flu-like symptoms are expected and should be treated supportively with acetaminophen and diphenhydramine as described above. If a patient cannot tolerate full dose IL-2 due to fevers, rash or constitutional symptoms, a dose decrease to 4 million units is allowed (2 million units/m² if < 45 kg). If the patient cannot tolerate the reduced dose, the IL-2 must be permanently discontinued.

IL-2 dosing guidelines for non-hematologic grade 3-4 toxicity (CTCAE v4):

Non-hematologic grade 3 toxicity persisting for > 24 hours: Hold IL-2. If the toxicity resolves to grade 2 or better within 48 hours, the IL-2 can be resumed at a reduced dose (4 million units or 2 million units/m² if < 45 kg). If the same toxicity persists, worsens or recurs, the IL-2 must be permanently discontinued. Missed doses are not made up.

Non-hematologic grade 4 toxicity: Permanently discontinue IL-2

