8.0 Study Calendar

The pre-treatment work-up must occur within 28 days (14 days for CBC, diff, CMP, and chemistries) of treatment start unless otherwise noted. Scheduled evaluations (including research samples) up to day +22 may be performed +/-1 day from the targeted date; evaluations and procedures (including research samples) performed after day +28 may be done +/-3 days of the targeted date. Follow-up for survival may be done +/- 4 weeks of the targeted date. In addition, targeted days may be altered as clinically appropriate.

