8.1 Patient

8.1.1 Standard of Care and Investigational Treatment

	Pre-Treatment (within 28 days of treatment start)*	During each treatment course					4-6 weeks after 2 nd treatment course	Follow-up at Day 90, 180, 270, 360	
		Day 1 ¹	Day 5	Day 15 or 17	During IL-2 administration (Day 17-22)	Day 24, 31, 38, 45			
EVALUATIONS									
Written consent	X								
Medical history	X								
Disease Characteristics	X								
Pathology review of outside dx	X								
Transfusion History	X						X		
Concomitant meds	X	X					X		
Physical exam	X	X	X ⁶	X ⁶	X ⁶	X ⁶	X		
Vital signs	X	X		X					
Weight	X	X		X	3 x a week during IL-2	X			
Height	X								
ECOG Performance Status	X	X					X		
Survival Status								X ⁷	
LABORATORY									
CBC w/ diff ²	X	X	X	X	daily during IL-2	X	X		
Na, K, Cl, CO ₂ , BUN, creatinine, uric acid, phos, LDH, Mg	X	X	X	X		X			
ALT/AST, bili, total protein, albumin, alk phos	X	X		X		X			
Chest X-ray	X								
INR/PTT	X								
Pregnancy test ³	X								
HLA typing (low resolution)*	X								
Recipient Viral Serology	X								
ECHO/MUGA*	X								
Bone Marrow Bx/Asp ⁴	X ⁴					X ⁵	X ⁴		
Investigational TREATMENT									
Decitabine IV		Day 1-5							
Vorinostat PO			Day 6-15						
NK cell infusion (research)				Day 17					
IL-2 tiw for 3 doses (research)					X (start Day 17)				

* CBC, dff, CMP, chemistries within 14 days of study treatment start, HLA typing may be done at any time

- 1- Course 1 Day 1 evaluations need not be repeated if pre-study evaluations were done within 14 days of 1st treatment
- 2- CBC with diff weekly throughout all treatment with increased frequency as clinically indicated
- 3- Women of childbearing potential only; serum or urine
- 4- Bone marrow aspirate and biopsy with standard flow cytometry, conventional cytogenetics, and MDS/AML FISH panel will be conducted at study initiation and at the completion of the 2nd cycle for standard disease assessment or at time of study withdrawal if early termination.
- 5- Prior to course 2 ONLY in patients who enrolled in this study as a prior treatment failure per section 4.2.2 or any patient who is discontinuing study treatment after 1 course
- 6- Clinical assessments will occur at a minimum of weekly up until the NK cell infusion on Day +17 after which clinical assessments will occur daily until the day after the final IL-2 administration.
- 7- By record review, patient contact, etc.

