9.0 Study Endpoints

This study is designed as a two stage study of the combination of Decitabine and Vorinostat and haploidentical NK cell infusion. The primary endpoint is clinical response (CR + PR + HI) at the end of the required 2 cycles of therapy. An assessment of response differences between untreated/minimally treated and those with prior treatment failures will be conducted.

The secondary endpoints include evaluation of safety tolerability, the proportion of patients who become transfusion independent, the association of the in vivo NK cell expansion with clinical response, and 1 year Overall Survival.

Clinical responses are defined in Appendix VI.

Determination of toxicities will be important for this new combination. As per NCI CTCAE Version 4.0, the term toxicity is defined as adverse events that are classified as either possibly, probably, or definitely related to study treatment. The maximum grade for each type of toxicity will be recorded for each patient, and frequency tables will be reviewed to determine toxicity patterns. In addition, we will review all adverse event data that is graded as 3, 4, or 5 and classified as either “unrelated or unlikely to be related” to study treatment in the event of an actual relationship developing.

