13.3 Statistical Analysis Methods

Ninety-five percent confidence intervals for the response probability were calculated using methodology reported by Duffy and Santner.⁴⁰

The summary statistics including 95% confidence intervals for toxicity rate and proportion of patients who become transfusion independent will be calculated. The association of in vivo NK cell expansion, as defined as persistence of donor NK cell chimerism at day +8, (yes or no) with clinical response will be estimated by chi-square test. Kaplan- Meier method will be used to estimate 1- year survival from the date of treatment. Given that the majority of patients will go on to receive additional therapy with either ongoing hypomethylating agents versus stem cell transplant, the estimates of 1 year overall survival from the point of study enrollment, will only be partially attributable to the study therapy and thus a minor focus of our statistical analysis.

SAS 9.2 (Cary, NC, USA) will be used for statistical analyses.

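### The 24-hour limit on the targeted-toxicity look-back leaves essentially none of the first day after each IL-2 injection on the form, losing mainly expected grade 1-2 reactions

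*Combined protocol and SAP*

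**What the plan says.** Section 11.2 lists six targeted assessments per course: before the NK infusion on day 17; once 1-2 hours after it, before IL-2; before IL-2 dose 2; before dose 3; 48 hours after dose 3 or at the day 24 visit; and one week after the last dose or at the day 31 visit. At each one, "the worst grade of the targeted toxicity since the last assessment or the previous 24 hours (whichever is shorter) will be recorded". The same section also states: "All time points are 24 hours +/- 2 hours".

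Other relevant text:

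- Section 7.5 gives IL-2 on days 17, 19 and 22. It says "Fevers, rash and flu-like symptoms are expected and should be treated supportively". It permits a lower dose under this condition: "If a patient cannot tolerate full dose IL-2 due to fevers, rash or constitutional symptoms".
- Section 8.1.1, footnote 6, sets weekly clinical assessments up to the NK infusion, "after which clinical assessments will occur daily until the day after the final IL-2 administration".
- Section 8.0 says scheduled evaluations "up to day +22 may be performed +/-1 day from the targeted date".
- The general table in section 11.2 does not require grade 1 events or expected grade 2 events to be documented.
- Section 9.0: "The maximum grade for each type of toxicity will be recorded for each patient". Section 13.3 plans this analysis: "The summary statistics including 95% confidence intervals for toxicity rate".

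**The concern.** No targeted assessment is listed for the day after an injection, and each one looks back at most 24 hours. A reaction that starts and ends within a day of the injection has no place on the form built to capture it.

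Safety and tolerability of outpatient NK cells with IL-2 is a secondary objective. If short expected reactions such as fever, chills, hypotension or rash are left off, the per-patient maximum grades of section 9.0, and any low-grade toxicity rate reported under section 13.3, are biased downward. Section 7.5 allows an IL-2 reduction for symptoms of this kind, so the form may also fail to show the reaction that preceded a reduction.

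**Working it through.** The plan gives no figure to reproduce here; the check is interval arithmetic on its schedule.

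**Inputs.** Time is in hours from IL-2 dose 1. Doses (section 7.5): 0, 48 and 120. Forms after IL-2 starts (section 11.2): 48, 120, 168 and 288. The form preceding dose 1 is taken as time 0.

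**Formula.** For a form at time t with the previous form at time p, the look-back runs from max(p, t - 24) to t. First-day coverage for a dose at time d is the overlap of that window with d to d + 24.

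| Form | Time (h) | Gap from previous form (h) | Look-back (h) | Position relative to latest dose |
|---|---|---|---|---|
| Before dose 2 | 48 | 48 | 24-48 | 24-48 h after dose 1 |
| Before dose 3 | 120 | 72 | 96-120 | 48-72 h after dose 2 |
| 48 h after dose 3 | 168 | 48 | 144-168 | 24-48 h after dose 3 |
| 1 week after dose 3 | 288 | 120 | 264-288 | 144-168 h after dose 3 |

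All four gaps exceed 24 h, so the limit applies every time. The first days are 0-24, 48-72 and 120-144 h. Their overlap with the windows is 0 + 0 + 0 = 0 of 72 h. Moving the last form to day 31 (336 h) changes nothing. From dose 1 to 48 h after dose 3, coverage is 3 x 24 = 72 of 168 h (43%).

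**Sensitivity to timing**

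| Reading | First-day hours covered, doses 1 / 2 / 3 | Total of 72 h | Earliest hour recorded after doses 1 / 2 / 3 |
|---|---|---|---|
| Nominal | 0 / 0 / 0 | 0 (0%) | 24 / 48 / 24 |
| Forms 2 h early | 2 / 0 / 2 | 4 (6%) | 22 / 46 / 22 |
| Forms 2 h early and a 26 h look-back | 4 / 0 / 4 | 8 (11%) | 20 / 44 / 20 |
| Forms 8 h early (assumed: morning visit, afternoon dose) | 8 / 0 / 8 | 16 (22%) | 16 / 40 / 16 |
| Both pre-dose forms a full day early (section 8.0 window) | 24 / 0 / 0 | 24 (33%) | 0 / 24 / 24 |

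The last row is the most generous, but section 11.2 says the day is to be adjusted to fit the time point, and that row still leaves doses 2 and 3 with nothing.

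**Other records.** The general table in section 11.2 requires all grade 4-5 events, unexpected grade 3 events, related non-hematologic grade 3 events and related unexpected grade 2 events. Section 11.3 gives stopping-rule events their own form. Appendix IX treats listed events as expected and attributable unless marked otherwise, so a grade 1-2 targeted reaction falls where the table requires nothing. The vorinostat log (Appendix VIII) covers ten days that end before IL-2 begins. A small remainder above grade 2 is also not required: expected grade 3 events that are hematologic or judged unrelated.

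**The case against.** Several points can fairly be made for the plan.

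- **The timing of reactions is not given.** Nothing in the documents says they end within a day, and the plan provides for some that last longer (section 7.5 has a rule for grade 3 toxicity beyond 24 hours). This stands against any estimate of size. It does not change the direction: a maximum over part of the time cannot exceed the maximum over all of it.
- **The loss is narrow.** Serious and higher-grade events, the primary endpoint and the stopping rule are unaffected. This stands and limits the severity.
- **The information should exist in source notes.** Daily clinic monitoring is required during IL-2. True, but no text ties those visits to a form, and the targeted form's own rule excludes what they find.
- **Section 13.3 names no grade for its toxicity rate.** The only rate given a hypothesized value is the grade 4-5 rate in section 13.2, which is safe. This stands; the exposed results are the section 9.0 maximum grades and any low-grade rate.
- **The form is not said to document reasons for IL-2 reductions.** This also stands; that consequence is only a possibility.
- **The 24-hour timing sentence might mean an assessment 24 hours after each dose.** That would close the gap, but it cannot be squared with listed time points at 1-2 hours, 48 hours and one week.

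**Conclusion.** The concern holds. At nominal times the targeted form records none of the first 24 hours after any IL-2 dose, and at most 11% with the +/- 2 hour wording. A reaction reaches the form only if it lasts beyond 24 hours after dose 1 or 3, or beyond 48 hours after dose 2. Under the clock-time variations up to 8 hours, at least the first 16 hours after doses 1 and 3 and the first 40 hours after dose 2 are still missed.

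The consequence is downward bias, of unknown size, in expected grade 1-2 tolerability results. Longer-lasting effects, such as weight gain or a creatinine rise, may still be seen. The result assumes dosing on days 17, 19 and 22 and forms at the listed time points; the 8-hour case rests on an assumed clinic timetable. This should be corrected, but it does not threaten the primary analysis or the safety stopping rule.

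**What to change.** Replace the look-back rule in section 11.2 with:

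> At the pre-NK time point of each course, the worst grade in the previous 24 hours will be recorded. At each later time point of that course, the worst grade since the last assessment will be recorded.

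Keep the existing clause on unexpected toxicities. Only the four assessments after IL-2 starts change, and the 24-hour baseline stays in both courses. First-day coverage rises from 0 to 72 of 72 hours, and coverage from dose 1 to 48 hours after dose 3 from 72 to 168 of 168 hours. Name the daily clinic visits during IL-2 as the source. Separately, state whether the 24 hours +/- 2 hours sentence is a timing tolerance or a look-back length, and make it agree with the listed time points.

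The cost is two sentences and any matching e-CRF instruction; Appendix IX carries no look-back text, and no visit is added. The drawbacks are:

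- slightly more chart review per form;
- five to seven days of recall for the last form, because daily visits end the day after dose 3;
- higher reported low-grade rates;
- windows of unequal length, so grades compare less directly between time points. This matters little when the planned summary is a maximum per patient.

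The section 8.1.1 calendar does not mark vital signs in the IL-2 column, so fever and blood pressure grades will depend on readings taken at the daily visits or on patient report.
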